#### Stability and User Perceptions of Stability:

Kinematic data collected by the motion capture system during the stand-to-fatigue and body weight distribution trials described above will be used to quantify the stability of the stimulation strategies.

Subjective perceptions of stability will be assessed with the Usability Rating Scale (URS). The URS will be adapted to assess subjective perception of stability and applied immediately after every standing test with each stimulation paradigm. Subjects rate only their impression of the task just completed and are not asked to make mental comparisons to past performance under the same or other conditions. Positive significant differences from zero of the change scores will indicate improved perception of stability while negative significant differences will indicate reduced perception of stability.

#### Discharge and Follow-up:

A user questionnaire will be administered prior to discharge to home to assess subjective satisfaction with the system. [7,8]. After discharge to home, medical conditions will be monitored on an ongoing basis via regular telephone or other means of electronic contact. While at home, the external controller for the implanted system will monitor patterns of usage and record the number and length of time each exercise or functional pattern is active. External controllers will be returned and exchanged for replacement units in a preventative maintenance program, at which time usage data will be downloaded and stored for later analysis [4].

Self-report of frequency and severity of pressure injuries, spasms, urinary tract infections and other medical conditions are monitored on a continual basis. Subjects may be requested to repeat the tests described above at follow-up intervals of approximately 6 to 12 and 18 to 24 months post-implantation. Data from the system monitor built into the External Control Unit will be downloaded during follow-up intervals.

Biomechanical tests of strength and endurance with continuous stimulation and each of the fatigue delaying stimulus paradigms will be repeated on the dynamometer. Elapsed standing times, body weight distribution and stability assessments may also be repeated as described above. Consistency of the stimulus parameters and biomechanical and clinical measures of standing performance will be assessed by comparing these follow-up results to baseline data pre-discharge.

Long term follow-up will include reapplication of the user questionnaire, and repeated measures of the medical and technical evaluations performed at intake. This may include repeat physical examinations, motor and sensory evaluation, bone density assessments and AP/Lateral images of the joints to document any changes due to weight bearing. The integrity and stability of the implanted components will be assessed through repeated measurements of surface potentials and

recruitment properties. Electrode performance will be evaluated by conducting standardized biomechanical measurements including stimulus thresholds and maximal stimulated manual muscle grades, in addition to the dynamometer and clinical tests of standing performance applied at the short-term follow-up interval. The SCI-QOL will be repeated at follow-up intervals after rehabilitation and training is completed for comparison against baseline ratings.

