At approximately 6 weeks post-surgery, or earlier if incisions are sufficiently healed, stimulated responses will be characterized and exercise with the implanted neuroprosthesis will be initiated. Recruitment properties (stimulus thresholds, manual muscle grades, spillover or reflex activation) of each electrode or contact within a nerve cuff will be recorded. The stimulated responses of the implanted electrodes will be incorporated into initial exercise patterns that will be constructed for each individual. Participants then begin a reconditioning program of progressive resistance strengthening and endurance exercises with stimulation customized to their rate of progress. The exercise program consists of established protocols for both strength training (few repetitions at maximal load via ankle weights) and endurance (high number of repetitions at low loads). These exercises may include contracting the muscles against loads using weights or resistive bands and commercially available exercise equipment. Subjects are expected to complete this exercise program prior to initiating standing, dynamometer and other tests of continuous stimulation or the fatigue delaying stimulation paradigms in order to ensure that their muscles are maximally conditioned and as fatigue resistant as possible.

Standing, pivot transfers and balance training follow the exercise phase until implant recipients demonstrate mastery of basic standing functions with the system, which can take several months. The users will undergo extensive training to learn basic sit-to-stand and quiet standing functions with continuous stimulation. A qualified clinical study staff may measure the strength and range of motion of the voluntary musculature and perform a full ASIA Sensory and Motor Evaluation during

follow-up approximately 1 year after discharge from post-implant rehabilitation. A follow-up DEXA may also be completed approximately 1 year post-rehabilitation to measure change in bone density.

Subjective ratings of physical and medical health, emotional health, social participation, and physical functioning will be obtained by administering a multiple-choice questionnaire, the Spinal Cord Injury-Quality of Life (SCI-QOL), at baseline and at follow-up intervals after rehabilitation and training is completed for comparison against baseline ratings.

Video recordings may be done during all experiments to help with data analysis and for display

during talks, seminars and workshops.

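### Does timing the repeat performance tests from implantation, rather than from the post-training baseline, undermine the stability comparison?

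*Combined protocol and SAP*

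**What the plan says.** Item 13, Discharge and Follow-up, says subjects may be asked to repeat the performance tests at "follow-up intervals of approximately 6 to 12 and 18 to 24 months post-implantation". Consistency of stimulus parameters and standing performance "will be assessed by comparing these follow-up results to baseline data pre-discharge". Item 10 names the same comparator: the first measurement after exercise and training.

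The two groups of tests carry different force. "Biomechanical tests of strength and endurance with continuous stimulation and each of the fatigue delaying stimulus paradigms will be repeated on the dynamometer", whereas "Elapsed standing times, body weight distribution and stability assessments may also be repeated as described above".

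For a new recipient, Item 13 puts these steps before that baseline:
- about 6 weeks of healing, or less;
- an exercise program whose length is not given;
- standing and balance training that ends at mastery and may run to several months;
- a tuning and testing phase of at most 50 days.

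Other measures are timed from the end of rehabilitation. The ASIA evaluation belongs to "follow-up approximately 1 year after discharge from post-implant rehabilitation". For bone density, "A follow-up DEXA may also be completed approximately 1 year post-rehabilitation". For quality of life, "The SCI-QOL will be repeated at follow-up intervals after rehabilitation and training is completed".

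**The concern.** The retest clock starts at surgery, while the measurement it is compared with is made later, at a time that differs between subjects. The longer a subject trains, the less of the first window is left after baseline and the shorter the interval it can cover. Nothing in the text stops a retest from following baseline by days.

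Stability over time is one of the four hypotheses in Item 9, and Item 10 checks stimulation parameters by comparing initial with follow-up values. Little change over a very short gap is weak evidence of stability, and the shortest gaps would go to the slowest trainees. Because the primary analyses are done subject by subject, other subjects' data would not make up for one uninformative interval. The post-rehabilitation timing of ASIA, DEXA and SCI-QOL makes the implantation anchor look like an oversight.

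**Working it through.** The protocol gives no derivation of its windows, so there is no planned figure to reproduce. The check is calendar arithmetic, with one month = 30.44 days.

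**Inputs from Item 13**
- Healing: 42 days.
- Testing phase T, upper limit: 50 days, read here as calendar days (the protocol does not say).
- Testing phase T, lower limit: 5 tuning sessions plus 4 conditions × 3 repeats = 12 test days, so 17 days. This assumes both legs and one stand are tested on the same day.

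**Assumed, not in the documents**
- Exercise E: 1 to 3 months.
- Standing training S: 2 to 6 months.

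**Baseline completion, in months after implantation:** B = (42 + T)/30.44 + E + S.
- T = 50: 92/30.44 = 3.02, so B = 3.02 + E + S.
- T = 17: 59/30.44 = 1.94, so B = 1.94 + E + S.

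**Break-even.** B passes month 6 when E + S exceeds 6 − 3.02 = 2.98 months (T = 50) or 6 − 1.94 = 4.06 months (T = 17). The whole first window is gone only when E + S exceeds 12 − 3.02 = 8.98 months (T = 50).

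**Intervals from baseline to retest**
- Fast (E = 1, S = 2, T = 17): B = 4.94. First window 6 − 4.94 = 1.06 to 12 − 4.94 = 7.06 months; second 13.06 to 19.06.
- Middle (E + S = 6): B = 7.94 (T = 17) or 9.02 (T = 50). Longest first interval 4.06 or 2.98 months; second 10.06 to 16.06, or 8.98 to 14.98.
- Slow (E = 3, S = 6, T = 50): B = 12.02. The first window is missed by 0.02 months, under one day; second 5.98 to 11.98.

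**Sensitivity**
- With no separate exercise time, the fast baseline moves to 1.94 + 2 = 3.94 months.
- If the 50 days are visit days at an assumed 3 per week, T = 50/3 × 7/30.44 = 3.83 months. The slow baseline is then 1.38 + 9 + 3.83 = 14.21 months, and the second window still follows it by 3.79 to 9.79 months.

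**What re-anchoring both windows would cost** (assumed range, calendar days)
- The second window would open at 18 + B = 22.94 to 30.02 months after implantation and close at 24 + B = 28.94 to 36.02, instead of 24.
- Item 19 gives a 7-year study, or 84 months. To reach the opening of the second window, a subject must now be implanted by month 84 − 18 = 66. After the change that becomes 84 − 22.94 = 61.06 down to 84 − 30.02 = 53.98.
- Item 22 foresees participation of up to three years, or longer if funding allows. Screening and preparatory exercise already use some of that before surgery.

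**The apparent precedent.** ASIA, and DEXA where it is done, have pre-implant baselines (Item 13, Screening). SCI-QOL is compared with a rating given at baseline, and the long-term medical and technical evaluations repeat those made at intake. None of these is timed from its own comparator, so they use a different anchor without showing the rule that the concern asks for.

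**The case for a change.** The strongest case for a change is that the break-even needs only document figures. Healing and full-length testing already take 92 days, and training alone may take several months, so passing month 6 before baseline is complete would be ordinary. A wide window lets staff book late but does not oblige them to. The wording for dynamometer retests is firmer than for standing tests, so the optional language does not settle the matter. For the 10 previously implanted volunteers (Item 13), windows counted from implantation may already have passed at enrolment.

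The timing facts stand, including the missing minimum interval. They do not show that trivial intervals are likely. Item 9 itself expects dynamometer retests at varying intervals, and the follow-up section makes retesting a matter of request at approximate times, which leaves room to place slow trainees late in the window and to fit in the earlier implantees.

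The present anchor also has a reason behind it. The one explicit initial-versus-follow-up test in Item 10 concerns pulse width and amplitude at the nerve-cuff contacts, and time since surgery is a defensible clock for an implanted interface. At long-term follow-up, electrode performance is checked "in addition to the dynamometer and clinical tests of standing performance applied at the short-term follow-up interval". If the performance tests moved and the implant checks did not, the two could need separate visits, and late enrollees kept on the old timing would leave the study with two schedules.

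**Conclusion.** No change is needed. The mismatch is real but small. At worst, some slow trainees' first-window comparison covers too short a time to say much about stability. Under exercise of 1 to 3 months, training of 2 to 6 months and calendar-day testing, the second window still gives 6.0 to 19.1 months after baseline. If the 50 days are visit days, its lower end is about 3.8 months. Losing the whole first window under the calendar-day reading needs every maximum at once, and then by less than a day against an approximate limit. The concurrent comparisons between paradigms, which are primary in Item 10, are untouched.

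Moving both windows would exchange this for later closure, dependence on funding, fewer subjects able to reach the second window, and mixed schedules. That is a trade-off with no clear gain. The baseline and retest dates will exist for every subject, and a competent analyst would give the actual interval beside each stability result without being told to. The training durations are assumptions, so the intervals are a range and not bounds.

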## 14. Will the research involve the following?

|     | N/A Chart/Data I                                   | leview |   |
|-----|--|---------------|---|
|     | Placebo Group                                      | ⊠ No          | Yes (describe):   |
|     | Other Control Group                                | ⊠ No          | Yes (describe):   |
|     | Randomization                                      | ⊠ No          | Yes (describe):   |
|     | Deception  | ⊠ No          | Yes (describe):   |
| 15. | Does the research invol
Information in any form |               | nd/or disclosure of Individually Identifiable Health
1?   |
|     | ☐ No ⊠ Yes   | If yes, com   | plete the required HIPAA Waiver/Authorization forms.  |
| 16. |  |               | ration of a study agent that does not require FDA approval itamins, food supplements, isotope tracers, alternative  |
|     | ⊠ No ☐ Yes -p                                      | rovide a deta | ailed description of the procedures used to assure patient safety.  |
| 17. |  |               | stered or will subjects be exposed to ionizing radiation?   |
|     | • Ex. Radiographic eq                              | uipment, fluc | proscopic equipment, and CT scanners, etc.  |
|     | review. Complete                                   | the "Applie   | Committee approval is required BEFORE IRB can cation for Human Subject Research Involving Ionizing and contact the Radiation Safety Officer at [contact] |

| 18. | In your judgment, could the objectives of the research be met in a way that presents less risk to subjects?  |
|-----|--|
|     | No ☐ Yes please explain:   |
|     | Section 4 – Subject Selection, Recruitment, and Vulnerable Populations   |
| 19. | Anticipated duration of entire study reported in years: 7 years.   |
| 20. | Estimated number of subjects to be studied at the LSCDVAMC or charts/records to be reviewed.   |
|     | • Provide answers for each cohort including normal controls; (patients, family members, treating physicians,):  |
|     | • 100 SCI subjects will be screened  |
|     | • 15 new subjects with SCI will be enrolled and receive the implanted neuroprosthesis  |
|     | • 10 previous recipients of implanted neuroprostheses.   |
| 21. | Estimated number of subjects to be studied or charts/records to be reviewed at all sites   |
|     | • Provide answers for each cohort including normal controls; (patients, family members, treating physicians,)   |
|     | N/A SINGLE SITE  |
| 22. | Duration of individual subject participation   |
|     | Provide answers for each cohort including normal controls; (patients, family members, treating physicians,).  |
|     | Individual participation for both newly implanted, and previously implanted subjects may last up to three years, or longer until study closure (dependent on available funding). |
|     | Chart/record review N/A  |
| 23. | Age range of subjects  |
|     | • provide answers for each cohort , including normal controls:  |
|     | Adults 18 years or greater   |
|     | Specific age range (list age range): 21 and over.  |
|     | ☐ Children -waiver from VACO: ☐ attached ☐ pending- provide submission date:   |
|     | **Contact AO/Research [contact] for guidance  |

| 24.                                  | Which of the following will be recruited or review   | ed for this study (check all that apply)?   |
|--------------------------------------|--|---|
|                                      | ∨ Veteran Inpatients   | Men Men   |
|                                      | ☑ Veteran Outpatients  | ⊠ Women  |
|                                      | ☐ Veteran Families   |   |
|                                      | *Normal volunteers   |   |
| app exp con por 4% reci coh con vete | *Non-Veterans; Provide justification SCI is proximately 250,000 persons in the US. At best 20 pected to be eligible for this study due to disqualify applications that would contraindicate participation obtained and envelope an | % of these individuals can reasonably be ing medical comorbidities and secondary. Furthermore, approximately 20% of the SCI ag the inclusion criteria would represent only amber of qualifying veterans necessitates approximately 20% of the study veterans which reflects the veteran will benefit greatly from the inclusion of non-             |
|                                      | *According to VHA Handbook 1605.04 Notice of P VHA Notice of Privacy Practices to all non-Veteran seeking care in humanitarian circumstances) receiving or non-Veteran research subjects enrolled in an appr Form 10-0483 Acknowledgement of the Notice of P Veteran research subject at the time of consent and g Once the Acknowledgement Form is signed please s information is needed please contact your Facility [contact] / [contact] [name]   | patients (e.g., active duty personnel or those ng care or treatment at a VHA health care facility oved VHA research study with clinical trials. VA rivacy Practices should be signed by the non-given a copy of the Notice of Privacy Practices. end a copy to the Privacy Officer. If additional rivacy Officers [name] or [name] |
| 25.                                  | Which vulnerable population(s) will be TARGET  | TED for recruitment in this study:  |
|                                      | • Indicate only those populations that are specin this document.   | cifically targeted for the research described   |
|                                      | 
 
It is not necessary to check any box if, for e
of subjects, some of whom may be elderly o
employees.
 
   | example, your study will include a full range
r subjects who might incidentally be   |
|                                      | ☐ N/A Chart Review (proceed to Item 30)  |   |
|                                      | NONE (proceed to Item 26)  |   |
|                                      | ☐ Medical students, house staff, or Employees of   | f the VAMC or Case  |
|                                      | Pregnant Women OR Women who are Breast   | feeding, Human Fetuses, or Neonates   |
|                                      | $\square$ Children – Complete Section 14 "Children as  | Research Subjects"  |
|                                      | Prisoners (The LSCDVAMC does not conduc  | t research involving prisoners)   |
|                                      | ☐ Targeting Persons over Age 65  |   |
|                                      | Persons with Acute/Severe Mental/Physical D  | isabilities (describe):   |

| Persons with Cognitive, Social, Economic, or Educational Disadvantages (describe):   |
|--|
| Others (describe):   |
| a. Provide the Scientific and Ethical reasons for Targeting these vulnerable populations in the research:  |
| b. What additional safeguards or provisions will be used to protect the rights and welfare of the
identified targeted vulnerable subjects?  |
| Surrogate consent  |
| Subject assent   |
| Use of a consent or Medical monitor  |
| Use of a waiting period  |
| A patient advocate will participate in the informed consent process  |
| Key elements of informed consent will be presented orally  |
| ☐ No supervisor or rater will be involved in obtaining consent   |
| Other - Describe Additional safeguards you plan to use:  |
| c. Describe the procedures used to ensure that the subject's legally authorized representative is
well informed regarding his/her role and obligation to protect persons with impaired
decision making capacity:                                 |
| 26. Procedures for Recruiting Subjects -check all that apply and attach all recruitment materials:  Not Applicable  Materials; Recruitment Letter, Posting on Bulletin Board, Brochure, Flyer, Post card, etc.   |
| Media; Internet Ads, Press Releases, Newspaper, Radio  |
| ☐ Investigator's Patient Population  |
| N Physician Referral   |
| Letters to Physicians/Clinicians   |
| Other (describe):  |
| 27. Will VA computer systems be used to identify potential subjects?   |
| e.g. VISTA, CPRS, Pharmacy Databases, other clinical databases, etc,   |
| No Yes-Describe how the computer will be used to identify patients. List all systems used and all information to be collected: VISTA/CPRS will be used to identify names, contact information, SSN, and medical history for eligibility determination. |
| 28. Will subjects be identified and/or recruited in clinics and/or inpatient wards at the LSDCVAMC?  |
| No Yes- explicitly describe your process for identifying and/or recruiting these   |

Physicians associated with SCI are aware of our studies and identify potential subjects who might meet the inclusion/exclusion criteria and are interested in FNS. If the subject is interested, contact information is exchanged. Volunteers will be recruited by integrating the screening and selection process for project participation into the routine for every patient admitted to the SCI Services of the LSCDVAMC.

| 29. In addition | to the consent form will any other materials be given to the subject?   |
|-----------------|---|
| □ N/A           | Chart/data review   |
| □ No            | Yes- check all that apply and submit for IRB review:  |
|                 | Letter  |
|                 | ☐ Information Sheets  |
|                 | ⊠ Questionnaire, Survey, Diary   |
| A broc          | ☑ Other (flyer, brochure, describe): A User Manual: Universal External nit for Lower Extremity Implanted Neuroprostheses -Revision 150521 hure titled: "Volunteering in Research" Questionnaire, and the Usability rating scale |

## 30. Please list by bullet point inclusion/exclusion criteria for the study.

- Entry criteria should be as detailed as necessary to define the subject population(s) under study and reduce confounding design. Include precise criteria for age, gender, and other relevant factors.
- List specific exclusion criteria which could interfere with the study design or place a subject at risk during the study.
- Provide answers for each cohort, including normal controls.

## Inclusion criteria for SCI participants:

- 1. Skeletal maturity (age 21 and above), and ability to sign informed consent
- 2. Paralysis resulting from neurological disorder such as low cervical/thoracic spinal cord injuries (C6-T12)
- 3. Time post injury greater than six months to assure neurological and emotional stability
- 4. Innervated and excitable lower extremity and lumbar trunk musculature
- 5. Absence of acute or unstable psychological problems, chemical dependency, or substance abuse.
- 6. Range of motion within normal limits, (full extension at the hip and knee, and ability to attain a neutral ankle position)
- 7. Controlled spasticity and absence of hip flexion and adduction spasms
- 8. Appropriate body habitus (not to exceed 300 lbs. or SCI-adjusted BMI less than morbidly obese.)
- 9. Adequate social support and stability
- 10. Willingness to comply with follow-up procedures.
- 11. Full coverage of the acetabulum and minimal knee and ankle laxity

SCI participants who previously participated in another surgical implant FES study may be considered for enrollment in this study.

